**Project secondary outcomes (readiness to change questionnaire to health providers):**

These data will be collected during baseline and post-intervention (Table 4). A self-administered questionnaire will be used, using paper forms. These forms will be sent to CLAP for data entry.

**Process Measures:** These will be used to monitor the implementation of the intervention and to assess compliance and protocol violations. A number of different strategies and data collection instruments are going to be used (see table 5).

- Data form, collected by data supervisors that will be sent to CLAP for data entry and validation.
- Monitoring of activities in the web portal, including a system to log the activities of birth attendants and opinion leaders.

## 9.2. Facilities

[figure not shown]
### 9.2.1. Computer Hardware and Software

Each hospital in the study will have a computer with the DMS installed and access to e-mail (Figure 2). At CLAP headquarters, a server and two terminals will be available for the study, equipped with the full version of the DMS. SPSS statistical software will be used for data analyses. The server will be provided with an uninterruptible power supply (UPS) and a disk array and backup system to assure data integrity.

## 9.3. Data Entry

Data collection forms (CLIN1, CLIN2, ALTA1 and ALTA2) are modified PIS forms that incorporate data particular to the study (that is not on the standard PIS) and hide the rest of the data. These forms are generated as a carbon copy of PIS. Every morning, the data clerk at the hospital level will collect all CLIN forms for deliveries of the previous day and all ALTA forms for all women that were discharged from the hospital that day. The data manager will then enter the data in the Remote Data Management Subsystem (RDMS) for that hospital. The RDMS is a standalone application that runs on a personal computer. Consistency checks are performed during data entry and warnings are displayed. The data is checked to make certain that entered values are acceptable, that all required fields are entered, and that items are consistent with other related items in the database. (see Appendix 4 for a detailed description of the DMS).

**Figure 3.** Data Management System components.

#### ***9.4. Data Editing and Error Resolution***

The database will incorporate routines for data validation (range and rules). If a validation rule fails during data entry, the data manager will be warned and will have the option to accept the value as correct, enter a new value, or generate an electronic query that can be corrected later. In any case, a validation log will be generated and recorded in the database. The log file will also record when the data was entered and by whom. This log will be used to review and audit the data management process (Appendix 4).

Most of the validation will be performed at the hospital level, using highly interactive procedures. Most problems should be solved while the clinical record is easily available. In most public hospitals in the region, it is very difficult and time consuming to access women's clinical records after the subject was discharged from the hospital. This problem can severely limit data quality because data validation queries produced after discharge are not answered. The present system will be designed in such a way that data entry and validation are performed simultaneously, while the clinical record is still available to check for inconsistencies detected by the program routines.

A second data entry will be performed at CLAP at the end of the data collection periods, and the DMS at CLAP will have a module to compare the first and second data entry to produce a validation report. The system will be designed in such a way that all modification to the database are registered in a log file (tracking). The data clerk at CLAP will review typing mistakes and will update the database, taking into account any updates made by the data manager at the hospital. The data in the log file will be used to this aim.

#### ***9.5. Transmission of Data***

Data and Validation Reports will be sent using an XML messaging system (Appendix 4) from hospitals to CLAP data center on a daily bases. At CLAP, the data will be reviewed, validated, and stored in backup files. Validated databases will be send to RTI, where the main study database will be held.

#### ***9.6. Security***

The system provides a secure environment for confidential medical information. Access to the system is limited to authorized individuals. The database is backed up on a regular basis. In addition, information that identifies the patient is stripped from the database when transmitted to CLAP CDD and RTI Data Coordinating Center (DCC). The server containing the study data will be provided with a UPS and a disk array and backup system to assure data integrity. The data center will limit access to CLAP personnel involved in data management and analysis.

#### ***9.7. Database Construction***

After closing the data collection, transaction files, master files, and validation reports will be reviewed. A final validation of data will be prepared and reviewed carefully. After the final cleaning of the data, several back-up copies of the computer files will be taken in a computer

file suitable for data analyses. RTI will hold and maintain the main study database until the end of the study. After completion of the study, a copy will be send to CLAP and UNC-CH for data analysis.

## **9.8. *Monitoring Data Collection***

CLAP data center will produce a number of reports to monitor data quality and trial progress (protocol compliance, quality of data at each center, completeness of data and completeness of women's set of forms, progress of recruitment, adverse event reports, etc.). Data quality control will also include medical record abstraction performed retrospectively. For each 3-month period, 1 day will be selected at random, medical records will be abstracted for all women who delivered that day, and data will be compared to the birth register. This will be performed during monitoring visits that will be made by the coordinating team at least once a year in each hospital.

## **9.9. *Reports***

### **9.9.1. *Data Monitoring***

During the 3-month data collection periods, the data management unit will produce detailed weekly and monthly data monitoring reports to assess data quality (missing and inconsistent data) and to monitor the number of patients that were included in study. These reports will present overall figures for the whole study and will also be stratified by hospital. These reports will be reviewed by the data manager and the study statisticians at CLAP, and they will be sent to the country data supervisor prior to their scheduled visits to the hospitals. If a severe problem is detected according to the reports, the country data coordinator will be contacted and will schedule a new visit to the center with the problem. A summary of the monthly reports will be also reviewed by CLAP study coordinator and the principal investigator.

### **9.9.2. *Steering Committee***

An annual summary report will be produced and sent to the Global Network Steering Committee. This report will include a summary of the annual figures for the following:

- Data Quality
- Protocol Violations
- Adverse Events

The year will be measured from May 1st to April 30th. For details on the contents of each report category, see below.

### **9.9.3. *Data Center***

The following reports will be periodically sent to RTI.

### **Data Quality Reports**

After each data collection periods, the data management unit will produce a summary report including

- number of patients that were included in the study in that period;
- missing data rates; and
- inconsistent data rates.

These reports will present overall figures for the whole study and will be also stratified by hospital.

### **Protocol Violations Report**

A specific report will be produced to account for potential protocol violations after each phase of the study or component of the intervention, as follows:

- Pre-randomization delivering of information to hospitals
- Selection of hospitals for randomization
- Presentation of the intervention at the hospitals and selection of opinion leaders
- Workshops
- Dissemination phase
- Implementation phase

The in-service training activities in the control hospitals will be reported simultaneously.

### **Adverse Events Report**

See section 9.9.5.

#### *9.9.4. NICHD*

The same reports that will be sent to RTI will be sent to NICHD.

#### *9.9.5. Adverse Events*

##### **Adverse Events in Health Providers (study subjects)**

- *Loss of job positions*
- *Malpractice lawsuits*

In case of an event of these types, a report will be produced and sent to the corresponding staff at the Data Center and NICHD, within 7 days of identification.

##### **Adverse Events in Women and Children**

###### *Maternal deaths*

In case of a maternal death, a report will be produced and sent to the corresponding staff at the Data Center and NICHD, within 2 days of identification.

*Neonatal Deaths*

A monitoring report on the number of in-hospital early neonatal deaths (up to 7 days of life) and the number of live births in the same period will be produced and sent to the Data Center and NICHD, on a monthly basis.

An annual summary report of the adverse events will be produced and sent to the Global Network Steering Committee.

## **10. Statistical Analysis**

---

### ***10.1. Analysis Plan***

Inference will be primary directed at the cluster (hospital) level. All analyses addressing the study research questions will use the “intention to treat” principle, thus comparing the original intervention group to the original nonintervention group, even if hospitals have withdrawn or shifted to another group. The data will be analyzed in collaboration by CLAP, UNC-CH, and the Global Network Data Center.

### ***10.2. Design Issues***

Episiotomy rate and active management rate will be assessed before randomization (baseline) and at the end of the intervention period in all hospitals (Table 4). As a subgroup analyses, the effect of the intervention on episiotomy rate will be assessed on primiparous women. Episiotomy and active management rates will be also measured 1 year after the end of the intervention period to assess the maintenance of the effect of the intervention.

### ***10.3. Sample Size***

A preliminary analysis of 1995-98 PIS data from 22 Argentinean hospitals showed a baseline frequency of episiotomies among vaginal deliveries of 42%, with a standard deviation of 11%. To protect against changes in the standard deviation (Lomas et al., 1991), we have based our sample size calculations on a standard deviation of 15%. Thus, we will need 18 hospitals (9 intervention and 9 control) to identify a decrease of episiotomy rates from 40% to 20%, with a 0.05 significance level and a 80% power. Our previous analyses of PIS data have shown that about 25% of deliveries are among primiparae, and 75% among multiparae. A reduction of the general episiotomy rate from 40% to 20% could be achieved by reducing the rate among primiparae from 80% to 40%, and the rate among multiparae from 26% to 13%. The rates after the intervention would be similar to the rates achieved in a previous trial (Argentine Episiotomy Trial Collaboration Group, 1993) and are thus potentially attainable. However, the sample size of 18 hospitals will allow us to identify a smaller decrease of episiotomy rates among primiparae vaginal deliveries, from 80% to 60%, with a 0.05 significance level and a 80% power. Assuming a baseline frequency of perineal sutures among primiparae of 85% with a standard deviation of 15%, our sample size of 18 hospitals will give us a power of 80% to identify a reduction of frequency of perineal sutures to 65%, with a 0.05 significance level.

We expect the use of oxytocin during the third stage of labor to increase from 10% to 50%. However, our sample size will allow us to detect smaller changes. Assuming a baseline frequency of injections of oxytocin of 10% and a standard deviation of 5%, the sample size of 18 hospitals will give us a power higher than 95% to identify an increase of use of oxytocin from 10% to 20%, with a 0.05 significance level. Assuming a baseline PPH incidence rate of 15% and a standard deviation of 5%, the sample size of 18 hospitals will give us a power of

84% to identify a reduction from 15% to 8%, and a power of 56% if the reduction were from 15% to 10%.

Hospitals will start the baseline data collection period before randomization to obtain data that will be used to assess the inclusion criteria (episiotomy and active management rate). If they fulfilled the inclusion criteria, they will then be randomized. A total of 24 hospitals will be included in this initial data collection to protect the study from hospital drop-outs and from the possibility of hospitals not fulfilling the inclusion criteria.

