## ***2.4.Secondary outcomes***

### *2.4.1. Clinical secondary outcomes*

- Perineal sutures rate among single vaginal deliveries.
- Incidence of postpartum hemorrhage >500ml among single vaginal deliveries.

Perineal sutures and hemorrhages will be studied to estimate the health impact of the intervention. Previous studies have established that selective use of episiotomy decreases the frequency of perineal sutures and that active management of the third stage of labor decreases hemorrhages. However, we will measure the effectiveness of their use in the context of our study.

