#### ***10.5. Analysis of Primary and Secondary Hypotheses***

At the group level, the primary outcome variable is the percentage of primary and secondary outcomes during the three months following the end of the intervention. Despite having only 12 observations in each arm, since each percentage is based on a large number of births, one can use the Normal approximation to the Binomial distribution, and thus the individual percentages can be assumed to be Normally distributed. This implies that when evaluating the efficacy of the intervention using the mean percentages at the end of the intervention period, the Student's t-test is appropriate and its use is justified. Baseline frequencies will also be presented, and baseline to follow-up ratios will be computed. Mantel Haenszel summary risk ratios combining the individual ratios for each hospital in the intervention group and non-intervention group will be computed. The intervention and non-intervention groups will then be compared at the group level using Student's t-test on the logarithms of the summary risk ratio (Wyatt et al., 1998).

In addition, the data collected at the individual level will be used to explore the potential for confounding of the main effects of the intervention due to imbalances arising from the group randomization. Such multi-level analyses will use mixed model techniques (Littell et al., 1996), also known as hierarchical linear models (Bryk and Raudenbush, 1992). These models account for the clustering effect and the intra-hospital correlation of the women from a given hospital. Furthermore, we will use descriptive statistics and GEE modeling (Diggle et al., 1994) to study the evolution of frequencies of outcomes between the four data collection periods.

For the analysis of provider's "readiness to change", the analysis will include three variables, one assessing "readiness to change" episiotomy, one assessing "readiness to change" management of third stage of labor and one assessing attitude toward changing practice in general. Ordinal scales will be used for the responses. Data will be summarized in terms of medians and interquartile ranges. Non-parametric statistics will be used to compare the pre- and post-intervention differences between the control and intervention groups."

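### Section 10.3 overstates the power of 18 hospitals by 4 to 5 points for the planned Student's t-test; 80% on episiotomy needs 20 hospitals, which the planned 24 still cover

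*Protocol*

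**What the plan says.** **Power (protocol section 10.3).** The unit is the hospital. For the overall episiotomy rate, "we have based our sample size calculations on a standard deviation of 15" per cent, and on that basis "we will need 18 hospitals (9 intervention and 9 control) to identify a decrease of episiotomy rates from 40% to 20" per cent, "with a 0.05 significance level and a 80% power". With the same 18 hospitals the section also claims:

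- 80% power for episiotomy among primiparae, from 80% to 60%;
- 80% power for perineal sutures, from 85% to 65%: "Assuming a baseline frequency of perineal sutures among primiparae of 85% with a standard deviation of 15" per cent;
- more than 95% power for oxytocin use, from 10% to 20%, SD 5%;
- for PPH with SD 5%, a power of "84% to identify a reduction from 15% to 8%, and a power of 56" per cent for a reduction from 15% to 10%.

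It adds that 24 hospitals enter baseline data collection, to allow for drop-outs and hospitals that prove ineligible.

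**Analysis (section 10.5).** Each hospital contributes one percentage per outcome. Because many births lie behind each percentage, it is treated as Normal, and the section concludes that "the Student's t-test is appropriate and its use is justified".

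**Suture outcome (section 2.4.1, repeated in 5.5.2.1).** "Perineal sutures rate among single vaginal deliveries". Section 10.2 plans an analysis among primiparae for episiotomy only.

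**The concern.** A power statement should describe the test that will be run. With 9 hospitals per arm the t-test estimates the between-hospital SD on 16 degrees of freedom, and a calculation with normal quantiles ignores the cost of that. The argument in section 10.5 that each hospital's percentage is nearly Normal supports using a t-test. It does not make the SD known.

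At stake is the number of hospitals said to be sufficient. Section 10.3 names 18 and enters 24, which reads as room to lose six and keep 80% power on a primary outcome. If 18 is too few, that margin is smaller than it looks.

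The suture figure raises a separate question. It describes a population, about 25% of deliveries by the protocol's own estimate, on which no suture analysis is planned in this document.

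**Working it through.** **Inputs.** All are from section 10.3 unless noted: alpha 0.05; n = 9 hospitals per arm; differences and between-hospital SDs of 20 and 15 points (episiotomy; sutures), 7 and 5 (PPH 15% to 8%), 5 and 5 (PPH 15% to 10%), 10 and 5 (oxytocin). Test: Student's t on hospital percentages (section 10.5). Sidedness is not stated. For primiparae episiotomy no separate SD is given; 15 points is assumed to carry over.

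**Step 1: reproduce the plan's figures.** Let λ = difference / (SD × √(2/n)). With n = 9, √(2/9) = 0.4714. Normal-approximation power is Φ(λ − 1.960).

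- Episiotomy: λ = 20 / (15 × 0.4714) = 2.828; Φ(0.868) = 80.7% (stated 80%).
- PPH 15% to 8%: λ = 7 / (5 × 0.4714) = 2.970; Φ(1.010) = 84.4% (stated 84%).
- PPH 15% to 10%: λ = 5 / (5 × 0.4714) = 2.121; Φ(0.161) = 56.4% (stated 56%).

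The matching sample size is 2 × [15 × (1.960 + 0.842) / 20]² = 8.83, rounded up to 9 per arm.

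One-sided calculations do not fit: the normal gives 88.2%, 90.7% and 68.3%, and the t gives 85.6%, 88.4% and 65.0%. A two-sided t-test with 10 per arm also fits (80.5%, 84.1%, 56.2%), but the text says 9 and 9.

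**Step 2: power of the planned test.** Power is the probability that a noncentral t with 2n − 2 degrees of freedom and noncentrality λ falls outside ±t(0.975). At n = 9 there are 16 degrees of freedom and the critical value is 2.120 instead of 1.960.

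| Comparison | Stated (18 hospitals) | Normal, 9 per arm | t, 9 per arm | t, 10 per arm | t, 12 per arm |
|---|---|---|---|---|---|
| Episiotomy 40% to 20%, SD 15% | 80% | 80.7% | 75.7% | 80.5% | 87.7% |
| PPH 15% to 8%, SD 5% | 84% | 84.4% | 79.6% | 84.1% | 90.6% |
| PPH 15% to 10%, SD 5% | 56% | 56.4% | 51.3% | 56.2% | 64.9% |
| Oxytocin 10% to 20%, SD 5% | above 95% | 98.9% | 97.8% | 98.8% | 99.7% |

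Simulation of 200,000 trials per scenario at 9 per arm gives 75.7%, 79.6% and 51.5% for the first three rows. The suture claim has the episiotomy inputs (20 points, SD 15%), so it is also 75.7%. So is the primiparae episiotomy claim if SD 15% applies to it.

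**Step 3: hospitals needed.** Adding the usual small-sample term 1.960²/4 = 0.96 to 8.83 gives 9.79, so 10 per arm or 20 hospitals; the exact power there is 80.5%. The reserve is 24 − 20 = 4, not 24 − 18 = 6, for an even split between arms.

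**Step 4: suture population.** Sections 2.4.1 and 5.5.2.1 use all single vaginal deliveries as the denominator; section 10.3 uses primiparae. The protocol gives no suture baseline or SD for all deliveries, so the power for the defined outcome cannot be computed from it.

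**Not checked.** Section 10.5 also plans a t-test on log summary risk ratios. No SD on that scale is given.

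**The case against.** **The trial as planned has enough hospitals.** Section 10.5 expects 12 observations per arm, where the t-test has 87.7% power on episiotomy. Oxytocin, the other primary outcome, is safe even at 9 per arm. This stands, and it makes the point one of correct statement and not of a deficient design.

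**The SD is already cautious.** Section 10.3 observed 11% and raised it to 15%. At 11% the t-test with 9 per arm has 95.1% power on episiotomy, and it stays at or above 80% up to an SD of about 14%. This also stands. But the claim is made at 15%, and at 15% it is not met.

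**The suture figure is openly labelled as primiparae, and sutures are a secondary outcome.** True, so it is a minor point. The reader is still left without a power figure for the outcome as defined.

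**Stronger readings that the protocol does not support.** A reader might infer that 18 is the lowest number at which the trial may proceed. No such rule is written: 18 is a computed requirement and 24 a reserve above it.

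A reader might also infer that falling below 18 is likely, because about 10% of surveyed hospitals were not above the 70% episiotomy cut-off and because an oxytocin mean of 10% with SD 5% puts about 16% of hospitals over the 15% exclusion limit. If the two are taken as independent and oxytocin use as Normal, the chance of fewer than 18 of 24 is 36%. But section 3.2.1 cites a survey average of 5% for active management. With that mean and the same SD the chance is about 2%. Section 3.2.1 also expects no exclusions. The range of 2% to 36% depends on assumptions the protocol does not make and cannot support a claim of probable loss.

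**Conclusion.** The powers stated for 18 hospitals are wrong for the planned test, except the one for oxytocin. The t-test gives 75.7% where 80% is stated, 79.6% where 84% is stated and 51.3% where 56% is stated. The computed requirement for 80% on episiotomy at SD 15% is 20 hospitals.

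This rests on a two-sided 5% test, equal arms and the protocol's own SDs. Both the two-sided test and the normal method are inferred from the fact that they reproduce the printed figures. On the other matching reading, a t-test with 10 per arm, 18 hospitals would still fall short.

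The consequence is limited. Power on episiotomy drops below 80% at SD 15% only if more than four of the 24 hospitals are lost. The one comparison that stays weak throughout is PPH 15% to 10%, at 64.9% even with 24 hospitals. The suture mismatch is real but secondary.

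**What to change.** Restate section 10.3 with power for the two-sided Student's t-test, and name the test and its sidedness:

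- 18 hospitals: 76% (episiotomy 40% to 20%), 80% (PPH 15% to 8%), 51% (PPH 15% to 10%);
- 20 hospitals, 10 per arm: the computed requirement for 80% on episiotomy at SD 15%;
- 24 hospitals: 88%, 91% and 65%.

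Correct the suture claim at 18 hospitals to 76%, and the primiparae episiotomy claim likewise, stating the SD used for it. Leave the oxytocin claim as it is. Say that the reserve within the 24 is four hospitals.

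For sutures, either give a baseline, SD and power among all single vaginal deliveries, or state that the primiparae figure does not apply to the outcome as defined.

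The cost is a change of wording and slightly less favourable figures. Hospital numbers, design and planned analyses stay as they are.
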